6.3 Post-Procedure

Post Clinical Assessments and Laboratory / Clinical Tests should be conducted per standard of care. Post-procedure information to be reported for this study include at minimum: adverse events, device performance, concurrent procedures, MR severity and NYHA Functional Class.

6.3.1 Final (Post-procedure) Imaging

Prior to discharge a TTE should be conducted per standard of care. The discharge TTE will be collected by the Sponsor for future reference and may be compared to baseline and/or follow-up TTEs.

6.4 Subject Follow-up

Follow-up is conducted per standard of care visits shown below. All follow-up assessment, visit or phone, should include a review for adverse events occurring since the last visit. Results from the KCCQ survey are required to be recorded and submitted at the 30-day and 12-month visits. Visit should be scheduled relative to the date of the MitraClip Procedure. If a 6-minute walk test is conducted as standard of and was conducted at baseline; results for 6-minute walk test at 30day and 12-months visits will be collected in the EXPAND Study.

Visits at:

- 30 days (30 days -14 days / +60 days)
- 12 months (365 days - 30 days / +90 days)

Phone call or visit at:

- 6 months (180 days - 30 days / +90 days)

6.4.1 Follow-Up Imaging

At the 30-day and 12-month follow-up visits a TTE should be conducted per standard of care. TTEs will be collected by the Sponsor for future reference and may be compared to baseline and/or follow-up TTEs.

During the follow-up period for this study (12 months) any unscheduled echocardiograms, either TEE or TTE, should be submitted to the Sponsor.

Table 2 outlines the assessment schedule for this study.

Table 2. Clinical Assessment Schedule

Required Assessments to be Collected	Pre-Treatment	Treatment	DIS	30-D	6-M	1-Y
				-14/+60 days	-30/+90 days	-30/+90 days
Informed Consent	X					
Medical History	X					
Medical Exam and Reporting of Vitals	X		X	X		X
NYHA Classification	X		X	X		X
KCCQ Survey	X			X		X
6 Minute Walk Test (Only if standard of care)	X			X		X
Adverse Events ¹		X	X	X	X	X
Transthoracic Echocardiography (TTE)	X	X ²	X	X		X
Transesophageal Echocardiography (TEE)	X	X ²				
Unscheduled Echocardiogram (TTE or TEE)			X	X	X	X

1. Adverse Events to be collected in this study include: cardiovascular events, device-related complications (as defined in section 4.2), and events classified as MAEs (as defined in section 4.1)
2. TTE and TEE during treatment should be submitted for the study only if capturing TTE and TTE echoes is part of standard of care.

7.0 ADVERSE EVENTS

To comply with worldwide standards and guidelines on clinical study adverse event reporting, Abbott has developed uniform and worldwide applicable standard definitions and reporting timelines to be used and adhered to by the investigators.

7.1 Definitions

7.1.1 Adverse Event

An adverse event (AE) is any untoward medical occurrence, unintended disease or injury, or untoward clinical signs (including abnormal laboratory findings) in subjects, users or other persons, whether or not related to the medical device.

Note 1: This definition includes events related to the device

Note 2: This definition includes events related to the procedures involved.

Note 3: For users or other persons, this definition is restricted to events related to the MitraClip® device.

An AE can therefore be any unfavorable and unintended sign (including an abnormal laboratory finding), symptom, or disease temporally associated with the use of a medicinal product, whether or not related to the medicinal product.

7.1.2 Serious Adverse Event

If the AE meets any of the criteria below, it is regarded as a serious adverse event (SAE).

- a) Led to a death,
- b) Led to a serious deterioration in health that either:
 - 1) Resulted in a life-threatening illness or injury, or

- 2) Resulted in a permanent impairment of a body structure or a body function, or
- 3) Required in-patient hospitalization or prolongation of existing hospitalization, or
- 4) Resulted in medical or surgical intervention to prevent life threatening illness or injury or permanent impairment to a body structure or a body function.

c) Led to fetal distress, fetal death or a congenital abnormality or birth defect.

A planned hospitalization for pre-existing condition, or a procedure required by the Clinical Protocol, without a serious deterioration in health, is not considered to be a serious adverse event.

7.1.3 Device Deficiency/Device Malfunction

Device deficiency (DD) is defined as an inadequacy of a medical device related to its identity, quality, durability, reliability, safety or performance, such as malfunction, misuse or use error and inadequate labeling. This includes the failure of the device to meet its performance specifications or otherwise perform as intended.

Note: Performance specifications include all claims made in the labeling of the device.

A device malfunction (DM) is the failure of a device to meet its performance specifications or otherwise perform as intended, when used in accordance with the IFU or protocol.

7.2 Device Relationship

Determination of whether there is a reasonable possibility that a product or device caused or contributed to an AE is to be **determined by the Investigator** and recorded on the appropriate eCRF form. Determination should be based on assessment of temporal relationships, evidence of alternative etiology, medical/biologic plausibility, and patient condition (pre-existing condition).

7.3 Adverse Event/Device Deficiency/Product Experience Reporting

7.3.1 Adverse Event Reporting

The Investigator will monitor the occurrence of AEs for each subject during the course of the clinical study and report as required by this Protocol. AEs need to be collected on the appropriate AE eCRF form. Additional information with regards to an adverse event should be updated within the appropriate case report form.

Adverse Events to be reported during this study include: all cardiovascular events, device-related complications (as defined in section 4.2), and events classified as MAEs (as defined in section 4.1). These AEs should be reported starting from the time that the MitraClip delivery system is introduced to the femoral vein through the 12-month follow up visit in cases with a MitraClip implant. In cases with an attempted MitraClip Procedure, but no implant, AEs are only collected through 30 days post attempted procedure.

The investigator should report all required SAEs to the Sponsor as soon as possible but no later than 3 calendar days from the day the study personnel became aware of the event or as per the investigative site's local requirements, if the requirement is more stringent than those outlined. The date the site staff became aware that the event met the criteria of a serious adverse event must be recorded in the source document.

A fax form will be made available to allow the investigator to report required SAEs in the event the entry cannot be made in the EDC. This does not replace the EDC reporting system. All information must still be entered in the EDC system as soon as feasible.

Serious adverse events that occurred in the user or persons other than the study subject should not be entered in the EDC system, however need to be reported via the Product Experience Report Form .

The Investigator will further report the SAE to the local IRB/EC according to reporting requirements.

7.3.2 Device Deficiency/Device Malfunction Reporting

All device deficiencies/malfunctions should be reported within the Electronic Data Capture (EDC) System on the appropriate eCRF form no later than 3 calendar days from the day the study personnel became aware of the event or as per the investigative site's local requirements, if the requirement is more stringent than those outlined.

A fax form will be made available to allow the investigator to report device deficiencies/malfunctions in the event that the entry cannot be made in the EDC. This does not replace the EDC reporting system. All information must still be entered in the EDC system as soon as feasible.

In case a device deficiency/malfunction occurred before *the patient ID has been assigned*, the device deficiency should be reported to the Sponsor via the Product Experience Report Form .

The device, if not implanted or not remaining in the subject, should be returned to Abbott.

Device deficiencies/malfunctions should be reported to the IRB/EC per the investigative site's local requirements.

7.3.3 Adverse Event Reporting to Country Regulatory Authorities by the Sponsor

The Sponsor will report the SAEs and DDs to the country regulatory authority, per local and regional requirements.

8.0 ADJUDICATION OF EVENTS

8.1 The Clinical Events Committee (CEC)

A Clinical Events Committee is comprised of qualified physicians who are not investigators in the study. The CEC will review and adjudicate pre-specified events reported by investigators or identified by the Safety & Surveillance personnel/designate for the study as documented in a CEC Manual of Operations (MOP).

9.0 STATISTICAL ANALYSIS

The following section describes the statistical methods for the clinical study. Details on statistical analyses are maintained in a separate Statistical Analysis Plan (SAP).

9.1 Statistical Overview

This is a post-market multicenter study of consecutive consenting patients have an attempted treatment with the MitraClip® NTR System and/or MitraClip® XTR System at participating centers. The study will include up to 1,000 subjects for analysis.

9.2 Analysis Populations

[REDACTED]

9.3 Sample Size Calculations and Assumptions

A sample size of 1000 subjects is expected to adequately capture data on a wide range of subjects with primary or secondary MR, subjects with or without complex valve anatomy, and subjects from Europe and the United States.

[REDACTED]

9.3.1 Planned Interim Analyses

There is no planned interim analysis to claim success of the study. Accumulating data from this study will be made public per the Publication Plan for the study.

9.4 Statistical Analyses

9.4.1 Endpoint Analysis

The intent of this study is to collect contemporary data in a real-world setting. All endpoints for this study will support a post-market assessment of device safety and performance. Descriptive analysis will be performed on the study data. Depending on the type of data (e.g., continuous or categorical), statistical methods described in this section below will be used.

For continuous variables, such as age, means, standard deviations, and 95% confidence intervals for the mean will be calculated.

For binary variables such as APS, counts, percentages, and 95% confidence intervals based on Exact Clopper-Pearson method will be calculated.

For time to event data such as all-cause mortality, Kaplan-Meier analyses will be performed.

For recurrent event data such as recurrent heart failure hospitalizations at pre- and post-procedure, data will be analyzed using a generalized linear model, such as Poisson regression model.

Results from this study will be presented within the context of the literature on the MitraClip.

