3.0 STUDY FLOW AND FOLLOW-UP SCHEDULE

3.1 Number of Subjects

Eligible consecutive patients that present for a MitraClip procedure should be consented. Once a patient has provided written informed consent, the patient is considered enrolled. Upon echocardiographic verification that there is no evidence of intracardiac, inferior vena cava (IVC) or femoral venous thrombus per IFU requirements; the MitraClip procedure should be attempted for all enrolled patients. A procedure is considered attempted when the MitraClip delivery system is introduced into the femoral vein. Only enrolled patients with an attempted MitraClip procedure will be included in the analysis population. Patients that have an attempted procedure, but no MitraClip implant will be followed for 30 days only.

Patients that do not give consent or patients with a thrombus identified on the pre-treatment echocardiogram are not eligible for the EXPAND Study and will not be part of the analysis population. If the thrombus is medically treated and resolved at a later date, a patient may be re-consented for the EXPAND Study if they are eligible for a new attempted MitraClip procedure.

Up to 1,000 consented subjects with confirmation of no thrombus who have a MitraClip procedure attempted will be included for analysis in *the MitraClip EXPAND Study*. The Study will be conducted at a maximum of 60 centers in the EU and the US. A site maximum of 100 subjects will be enforced so that no site will be permitted to submit data for more than 10% of the study population.

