4.2 Clinical Endpoints

Clinical Endpoints will be assessed at each study time point, all data reported at the corresponding study visit will be included for the study time point.

- Major Adverse Events (MAE): defined as a composite of CEC adjudicated all-cause Death, Myocardial Infarction, Stroke, or non-elective CV surgery for device related complications
- MR Severity
- Device Related Adverse Events (including mitral valve stenosis, device embolization, single leaflet device attachment (SLDA), iatrogenic atrial septal defect, myocardial perforation, or the need for mitral valve replacement instead of repair due at least in part to the MitraClip procedure or the presence of the MitraClip device)
- All-cause mortality
- Recurrent heart failure hospitalization
- New York Heart Association (NYHA) functional class improvement

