5.2 Subject Screening and Informed Consent

5.2.1 Subject Screening

The hospital will follow their standard of care procedures for determining if a patient is eligible for treatment with a MitraClip System. Consecutive patients who present for their procedure should be asked to provide consent for participation in the MitraClip XTR PMCF Study if they are eligible per the inclusion/exclusion criteria. Only patients that have a MitraClip XTR implanted will be included in the analysis.

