9.4 Statistical Analyses

Descriptive analysis will be performed on baseline, APS, clinical and safety event data. Depending on the type of data (e.g., continuous or categorical), statistical methods described in this section below will be used.

For continuous variables, such as age, means, standard deviations, and 95% confidence intervals for the mean will be calculated.

For binary variables such as APS, counts, percentages, and 95% confidence intervals based on Exact Clopper-Pearson method will be calculated, and p-values may be presented for hypothesis generating purposes.

For time to event data such as all-cause mortality, Kaplan-Meier analyses will be performed.

For recurrent event data such as recurrent heart failure hospitalizations at pre- and post-procedure, data will be analyzed using a generalized linear model, such as Poisson regression model. A p-value to measure the strength of evidence may be provided for descriptive purposes.

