2.3 Endpoints Analyses

Study endpoints defined in section 1.4 will be summarized descriptively using methods described in Section 2.2.Sample

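### Poisson regression is the only model named for pre/post heart failure hospitalisation counts, yet the protocol's own earlier counts are overdispersed and follow-up time is unequal; robust variance clustered on patient and a person-time offset should be specified

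*Protocol*

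**What the plan says.** Protocol 9.4.1 covers recurrent heart failure hospitalisations before and after the procedure in one sentence: "data will be analyzed using a generalized linear model, such as Poisson regression model". PMCF section 9.4 (Protocol Appendix I) has the same sentence and adds: "A p-value to measure the strength of evidence may be provided for descriptive purposes". Poisson is the only model named, and only as an example.

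Protocol 9.0 leaves statistical detail to the SAP. SAP 2.3 reads: "Study endpoints defined in section 1.4 will be summarized descriptively using methods described in Section 2.2". The visible parts of SAP 2.2 are descriptive statistics, Kaplan-Meier and logistic regression. The only censoring rule, in SAP 2.2.2, is for time-to-event data. No visible text gives an offset, a variance method, a link between a patient's two periods, or a look-back length. Protocol 6.1.2 collects the history of these admissions at baseline without stating a period.

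On follow-up time:
- Protocol 7.3.1 collects events "through the 12-month follow up visit in cases with a MitraClip implant". Protocol 6.4 allows that visit from day 335 (365 − 30) to day 455 (365 + 90).
- Protocol 3.1: "Patients that have an attempted procedure, but no MitraClip implant will be followed for 30 days only". The PMCF differs (PMCF 5.2.1): "Only patients that have a MitraClip XTR implanted will be included in the analysis".
- PMCF 4.2: "all data reported at the corresponding study visit will be included for the study time point".
- After withdrawal, only vital status is recorded (Protocol 5.5).

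**The concern.** A Poisson model sets the variance equal to the mean. Heart failure admissions usually cluster in a few patients, and here each patient contributes a count to both periods. If the model is run as named, the interval for the pre/post rate ratio can be too narrow, and so can the basis for the p-value that the PMCF allows.

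The second issue is person-time. A ratio of raw counts treats both periods as equally long for everyone. Death, withdrawal and 30-day-only follow-up shorten the post-procedure period and make the later count look lower. Late 12-month visits lengthen it and push the other way.

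At stake is how the result reads beside earlier work. Protocol 9.4.1 promises presentation in the context of the MitraClip literature, and the EVEREST II High Risk Registry reported rates per patient-year (0.65 to 0.36) over one year before and one year after.

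**Working it through.** The plan has no design figure for this analysis to reproduce. The check uses figures quoted in Protocol Appendix IV.

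**1. Are the earlier counts Poisson?** REALISM High Risk gives 402 events with 36.6% of patients hospitalised before, and 174 events with 17.8% after. The denominator is not stated; I assume the 628 enrolled.

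- Poisson expectation, P(≥1) = 1 − exp(−μ):
  - before: μ = 402/628 = 0.640, so 47.3% expected against 36.6% stated;
  - after: μ = 174/628 = 0.277, so 24.2% expected against 17.8% stated.
- A homogeneous Poisson would need 402/−ln(0.634) = 882 or 174/−ln(0.822) = 888 patients. A denominator below 628 would strengthen the finding.
- Deaths and 30-day-only follow-up alone would lower the post-procedure expectation only to 23.8%.

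**2. How overdispersed?**

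- Lower bound with no distribution assumed (every hospitalised patient has 1 or 2 events, with m events on average): E[X²] = p[(2 − m) + 4(m − 1)].
  - before: m = 1.749, variance/mean = 1.22;
  - after: m = 1.557, variance/mean = 1.44.
- Negative binomial, solving (1 + kμ)^(−1/k) = 1 − p:
  - before: k = 1.416, variance/mean = 1 + kμ = 1.91;
  - after: k = 3.349, variance/mean = 1.93.

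**3. Effect on the pre/post log rate ratio.** Let V be variance/mean and r the correlation of patient frailty between periods.

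- Variance = [V1/μ1 + V2/μ2 − 2r√(k1k2)]/628.
- Plain Poisson variance = 1/402 + 1/174, so SE = 0.0907.
- Actual coverage of a nominal 95% interval = 2Φ(1.96/factor) − 1.

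| r | SE factor, negative binomial | coverage | SE factor, minimum dispersion (k = (V − 1)/μ) |
|---|---|---|---|
| 0 | 1.39 | 84% | 1.17 |
| 0.5 | 1.22 | 89% | 1.11 |
| 1 | 1.04 | 94% | 1.04 |

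For the observed ratio 174/402 = 0.43, the plain Poisson interval is 0.36–0.52. The negative binomial interval is 0.34–0.55 at r = 0 and 0.36–0.52 at r = 1.

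A simulation (1,000 patients, no true change, mean 0.64 in each period) agrees. With independent frailty, type I error is 15.6% for plain Poisson and 5.2% with robust variance clustered on patient. With shared frailty, both give 5.1%.

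**4. Person-time.** Assume a constant death hazard λ and a one-year look-back, with survivors observed to day d. Mean years = (1 − exp(−λd/365))/λ. A non-implanted share n contributes 30/365 year. REALISM deaths run to day 410, so there λ = −ln(1 − m)·365/410, with m now the proportion dead.

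| Source | Mortality input | n | Loss, d = 365 | Loss, d = 395 (mid-window, assumed) |
|---|---|---|---|---|
| GRASP | 11/117 | 0 | 4.8% | −2.6% (gain) |
| REALISM Non-High Risk | 27/271 | 4.8% | 8.7% | 1.6% |
| Sentinel | 15.3% | 0 | 7.9% | 0.9% |
| TRAMI | 20.3% | 3% | 13.0% | 6.7% |
| TVT linked | 25.8% | 0 | 13.5% | 7.5% |
| REALISM High Risk | 146/628 | 4% | 14.1% | 8.0% |

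Applied to the earlier registry's ratio 0.36/0.65 = 0.55, a raw count ratio would read 0.53 to 0.48 at d = 365, and 0.57 to 0.51 at d = 395.

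**The case against.** The plan is not bound to plain Poisson. It commits to a generalized linear model and gives Poisson as an example, which leaves room for negative binomial, quasi-Poisson, GEE and an offset. A reader might infer that raw counts will be compared and the benefit inflated. No passage says so, and the sponsor's precedent is a rate per patient-year. This stands: the missing offset and look-back are missing detail, not an error.

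A reader might also conclude that the SAP omits the method. That cannot be shown. SAP 2.1.1 is blank, reference 3 is listed but never cited in visible text, and 2.2.3 starts without a lead-in. The SAP also names a different plan number (ABT-CIP-10236) from the protocol's 17-518. The eCRF, which may fix the look-back, is not supplied.

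The exposure inputs are soft. Protocol 9.2 is redacted and the SAP acronym list includes an implanted population, so 30-day-only patients may not enter, although Protocol 3.1 puts attempted cases in the analysis population. The upper end hardly moves without them: TVT linked, with n = 0, still gives 13.5% and 7.5%. The GRASP denominator is uncertain, because the same account gives 4 events as 4.3% and 4/117 is 3.4%. The PMCF follow-up table prints an upper limit of +9 days for the 1-year visit against +90 in the main protocol; if +9 is meant, late visits offset little there.

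Overdispersion within each period does not by itself make a paired comparison too narrow. If patient heterogeneity is fully shared, nearly all of it cancels. This stands too, and is why the result is a range.

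**Conclusion.** The point holds as a minor improvement to a descriptive analysis. Run as named, plain Poisson would understate the standard error of the log rate ratio by a factor of 1.04 to 1.39, with coverage of 94% down to 84%. The shortfall is negligible only if heterogeneity is almost fully shared between periods. This rests on REALISM High Risk being a fair guide, on 628 as denominator, and on the negative binomial form; at minimum dispersion the upper factor is 1.17.

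Person-time is needed because follow-up is unequal by rule and by death. Without it the bias is modest: between a 2.6% gain and an 8.0% loss of person-time once late visits are netted at an assumed day 395. A claim that omission must favour the device is not supported.

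Nor is a main-study endpoint or a success claim at risk. Recurrent heart failure hospitalisation is a listed endpoint in PMCF 4.2. In the main study, recurrent counts appear only as an example of a data type; the listed clinical measure is heart failure hospitalisation, and Kaplan-Meier with censoring would handle unequal follow-up for first events. The PMCF p-value is optional, and PMCF success rests on acute procedural success alone.

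**What to change.** Replace the example wording in Protocol 9.4.1 and PMCF 9.4, and carry it into SAP 2.2, with text such as: *Heart failure hospitalisation counts will be analysed by a log-linear model with period as covariate, log person-time as offset, and GEE robust variance clustered on patient. The pre-procedure look-back is a stated length equal to the period for which these admissions are collected at baseline. Post-procedure time ends at the earliest of death, withdrawal, last contact or a fixed day, and only events within that time are counted. Rates are reported per patient-year.* A negative binomial model with a patient effect is an acceptable alternative. A one-year look-back, if the baseline data support it, would match the earlier high-risk registry.

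If redacted SAP text or the eCRF already states the offset and look-back, the sponsor need only point to it.

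The cost is a few sentences and standard SAS procedures. Exposure dates must be used, and the interval may widen.
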